5.2 Visits and Assessments

Refer to [Appendix 1](#) for a detailed schedule of study procedures and events by visit.

5.2.1 Screening Visit

Subjects being considered for the study will be consented prior to hospital discharge, and screening procedures will then be performed while the subject is hospitalized to determine eligibility for treatment. Local laboratory testing was to be used for screening to determine inclusion and exclusion criteria have been met, prior to initiating treatment. Local laboratory tests performed for screening purpose only will be kept in subjects' source documents but will not be entered into the eCRF. In addition, Central Laboratory testing will be collected for the purpose of safety assessment and data analyses. For ineligible subjects, demographic data and ineligibility reason(s) will be captured.

5.2.2 Treatment Day 1

Subjects will be randomized and receive treatment within 3 days (72 hours) of Screening. Randomization can occur while the subject is hospitalized or after discharge from the hospital. All assessments and activities will be performed on Day 1 prior to Albutein treatment. In the SMT + Albutein 20% treatment group, vital signs and serum albumin

Effective Date	09-Sep-2024
Page	15 of 52

Number	BIG-CL-SP-000319
IG1601 Statistical Analysis Plan	

GRIFOLS	Bioscience Industrial Group
---------	-----------------------------

Number	IG1601 Statistical Analysis Plan		
	Version	2.0	Status
Effective Date	09-Sep-2024	Effective	Page
			16 of 52

concentration will also be recorded after Albutein treatment.

5.2.3 Treatment Day 11 and Monthly Visits (Month 1 through Month 11)

Subjects will have assessments on Day 11 (± 2 days), Month 1 (± 2 days), and then monthly (± 2 days) for up to 11 months: Days, 61, 91, 121, 151, 181, 211, 241, 271, 301, 331 (See [Section 5.2.5](#) for Day 361 assessments). All assessments and activities will be performed prior to Albutein treatment for the SMT + Albutein 20% treatment group. In addition, for the SMT + Albutein 20% treatment group, vital signs and serum albumin concentration will also be recorded after treatment.

5.2.4 SMT + Albutein 20% Treatment Days 21, 41, 51, 71, 81, 101, 111, 131, 141, 161, 171, 191, 201, 221, 231, 251, 261, 281, 291, 311, 321, 341, and 351

Subjects in the SMT + Albutein 20% treatment group will receive Albutein infusions every 10 (± 2) days for up to 12 months in the study. All assessments and activities will be performed prior to Albutein infusion, and in addition vital signs will also be recorded after Albutein infusion. These treatment day visits apply to the SMT + Albutein 20% treatment group only; subjects in the SMT treatment group will not have assessments on these study days.

5.2.5 Month 12 / Early Discontinuation

All subjects will have assessments at Month 12 (Day 361 ± 2 days)/Early Discontinuation. Subjects in the SMT + Albutein 20% treatment group will receive an Albutein infusion at Month 12. All assessments and activities will be performed prior to treatment for SMT + Albutein 20% treatment group. In the SMT + Albutein 20% treatment group, vital signs and serum albumin concentration will also be recorded after Albutein infusion.

Subjects who discontinue from the study early will complete the assessments that are planned for the Month 12 visit.

5.2.6 End of Study for Completed Subjects

Subjects who complete the full 12 months of treatment will return within one week of study completion for collection of prior/concomitant medications and adverse events (AE).

5.2.7 Follow-Up for Early Discontinued Subjects (Months 3, 6, and 12)

In subjects who discontinue from the study early, data on liver transplantation, subject survival, and cause of death will be obtained at Months 3, 6, and 12.

5.3 Treatment Administration

5.3.1 Albutein 20% Dosage, Procedures, and Treatment Regimen

Randomization must occur within 3 days (72 hours) of screening, and it can occur while the subject is hospitalized or after discharge from the hospital. The first Albutein 20% infusion is administered on the same day as randomization at a dose of 1.5 g/kg body weight (maximum 100 grams per infusion). Thereafter, subjects will receive Albutein 20% infusions at the dose of 1.5 g/kg body weight (maximum 100 grams per infusion) every 10 ± 2 days for the rest of the study (up to a maximum of 12 months). At each administration, the maximum infusion rate should not exceed 4 mL/min. Reasons for any deviation from the administration of less than 100% of the IP dose as prepared by the pharmacist or designee must be recorded.

5.3.2 Standard Medical Treatment

Following randomization, subjects randomized to the SMT alone group will receive SMT, which will be administered per institution standards. Several guidelines are published for the management of decompensated cirrhosis (12-15).

5.4 Study Variables

5.4.1 Efficacy Variables

The following efficacy variables will be assessed in this study:

Primary efficacy

- Time to liver transplantation or death through 1 year after randomization

Secondary efficacy

- Time to liver transplantation or death through 3 and 6 months after randomization, and time to death through 3 and 6 months after randomization
- Time to death through 1 year after randomization
- Total number of paracenteses and incidence of refractory ascites according to the ICA criteria

Exploratory efficacy

- Incidence of ACLF (3, 6, and 12 months)
- Organ function sub-scores (liver, renal, cerebral, coagulation, circulation, and respiration), according to the CLIF-C OF score
- Number and length of hospital readmission for an acute complication of cirrhosis
- Number and length of ICU admission

GRIFOLS	Bioscience Industrial Group	Number	BIG-CL-SP-000319
		Version	2.0
IG1601 Statistical Analysis Plan		Status	Effective
		Effective Date	09-Sep-2024
		Page	17 of 52

Number	BIG-CL-SP-000319		
Version	2.0	Status	Effective
Effective Date	09-Sep-2024		
Page	18 of 52		

- Incidence of disease-related complications (anticipated disease progression includes, but not limited to HE, GI bleeding, portal hypertension, ascites, SBP, hyponatremia, and HRS)
- Serum albumin concentration and albumin functional capacity in serum (albumin binding capacity)
- Incidence of insertion of TIPS for refractory ascites
- CLIF-C ACLF score, CLIF-C AD score, MELD score, and Child-Pugh score
- Quality of life: EQ-5D-5L health questionnaire

5.4.2 Safety Variables

The following safety variables will be assessed in this study:

- The number of suspected adverse drug reactions (ADRs; defined as possibly and or definitely drug related), including ARs (defined as definitely drug related), and incidence rate of subjects with suspected ADRs during the treatment period and within 72 hours after Albutein 20% infusion completion (or after Albutein 20% infusion stops) will be considered as the main safety variables. Due to the open label design of this trial, ADRs will be assigned causality to Albutein and ADRs will not be applicable to SMT.
- The number and incidence rate of overall treatment-emergent adverse events (TEAEs) and Serious AEs (SAEs), in addition deaths and discontinuations due to AEs will be also collected and analyzed.
- Clinically significant/relevant changes in vital function and clinical laboratory testing parameters, as determined by the investigator, will be documented as AEs and reported as part of the adverse event summaries.
- Vital signs (temperature, blood pressure, heart rate, respiratory rate) at each scheduled visit and, in particular before and after each Albutein 20% administration.
- Clinical laboratory test parameters including:
- Chemistry (Sodium, potassium, creatinine, blood urea nitrogen (BUN), calcium, magnesium, lactate dehydrogenase (LDH), aspartate aminotransferase (AST), alanine aminotransferase (ALT), gamma-glutamyl transpeptidase (GGT), alkaline phosphatase (ALP), glucose, total bilirubin, direct and indirect bilirubin, C-reactive protein (CRP), serum albumin [pre and post albumin 20% infusion in the SMT + A20% group])
- Hematology (Hemoglobin, hematocrit, platelets, red blood cell count, white blood cell (WBC) count with differential, total neutrophils, lymphocytes, monocytes, eosinophils, basophils)
- Lactate
- Coagulation (International normalized ratio (INR), fibrinogen, prothrombin time)
- Albumin functional capacity assessment (Albumin binding capacity)
- Urine pregnancy test (Qualitative urine β -human chorionic gonadotropin [β -HCG])
- Procalcitonin
- Biomarker (interleukin [IL] 6 (IL-6), IL-8, IL-10) and tumor necrosis factor alpha [$TNF\alpha$])

Number	BIG-CL-SP-000319		
	IG1601	Statistical Analysis Plan	
Effective Date	09-Sep-2024	Status	2.0
Effective	19 of 52		
Page			

- Plasma biomarker retains and transcriptome
- Physical examinations

6 General Statistical Considerations

All analyses will be conducted using SAS Version 9.4 or higher.

Unless otherwise noted, for continuous variables, descriptive statistics for continuous/quantitative data will include the number of non-missing values, mean, standard deviation, median, 25th percentile (Q1), 75th percentile (Q3), minimum and maximum. In general, the mean, median, Q1 and Q3 will be presented to one decimal place greater than the original data, standard deviation will be 2 decimal places greater than the original data, and the minimum and maximum will have the same number of decimal places as the original data. For categorical/qualitative data, descriptive statistics will include counts and percentages (rounded to 1 decimal place) per category.

6.1 Data Handling

6.1.1 Missing Data Imputation

Unless otherwise noted, if an observation is missing at a specific scheduled visit/time point, the value at that visit will not be imputed and will be set to missing.

For the time to event endpoints, early discontinued subjects will be followed up at month 3, 6, and 12 to collect information on liver transplantation, subject survival, and cause of death, subjects who do not have an event relating to an event endpoint within the analysis period will have their time to event censored at the earlier of date of last contact or cut-off date for analysis.

For longitudinal efficacy outcomes, the mixed-effects model for repeated measurement (MMRM) and generalized linear model implemented in SAS proc Genmod will be used to model the incomplete data. Missing data will be not explicitly imputed.

6.1.2 Day 1 Definition and Study Drug Administration

Subjects randomized to SMT + Albutein 20% are scheduled to have their first infusion on the date of randomization. For SMT + Albutein 20% subjects, Study Day 1 will be considered as the first infusion date. Subjects randomized to SMT are assumed to already be receiving SMT per institutional standards at the time of randomization. They receive treatment per the investigator's treatment plan for the subject under their institutional standards for SMT and the Day 1 study visit is considered as the Study Day 1.

For primary and secondary time to event endpoints the date of randomization will be used as the start of the time period.

All concomitant medications for both treatment groups are collected and classified as either SMT or other in the electronic case report form (eCRF). The first post-randomization date of any medication(s) given as SMT is collected.

6.1.3 Definition of Baseline

Baseline is defined as the last measurement taken prior to the start of study treatment for the SMT + Albutein 20% group and for the SMT alone group baseline is the last measurement taken on or prior to the Day 1 visit. For SMT + Albutein 20% subjects, two sets of vital signs assessments are collected on day of first infusion; the vital signs assessment time will be used to determine whether the vital signs were collected pre- or post-Albutein administration if assessment time is not available, then the vital signs designated by the investigator as pre-dose on the eCRF will be considered baseline. For all other assessments, if time of assessment is not available then an assessment that occurs on the same date as randomization is assumed to be prior to randomization and considered baseline.

6.1.4 Definition of Last Subject Contact Date

The last contact date is defined as the last observation recorded in the eCRF or other sources of study data (e.g., laboratory data) which provide proof of being alive. The following lists the dates to be considered for status of being alive.

- Date of visit (regular and unscheduled visits)
- Study drug infusion start date
- Liver transplant date
- AE start date
- AE end date, with Outcome not “Fatal”
- TIPS insertion date
- Hospital admission date
- Paracentesis procedure date
- Hospital admission date
- Disease-related complication date
- Blood product start date
- Prior/concomitant medication start/end date
- Date of subject completion or withdrawal
- Date of liver transplant/vital status assessment, with survival status not “Dead”

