5.3.5 Follow-up of Subjects Withdrawn from Study

If possible, blood samples will be obtained to complete all pertinent tests at the time of subject withdrawal. In all cases, the reason for withdrawal must be recorded in the eCRF and in the subject's records. No subject can be re-enrolled into the study after having been withdrawn from the study.

Subjects who receive any amount of IP and discontinue early from the study should have all Month 12/Early Discontinuation visit procedures performed at the time of withdrawal (preferably within 1 week of withdrawal).

All efforts should be made to collect the vital status of the subject (including data on liver transplantation, subject survival, and cause of death) at Months 3, 6, and 12.

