- ^f Clinical laboratory assessments will include hematology, chemistry, and coagulation performed by the central lab. At the Screening visit only, local laboratory tests will be performed in order to determine subject eligibility. Screening local laboratory test results will be kept in subjects' source documents but will not be entered into the eCRF (see Table 7-1).
- ^g Serum albumin concentration will be measured immediately prior to treatment. In the SMT + Albutein 20% treatment group, serum albumin concentration will also be measured immediately after the end of the Albutein 20% administration.
- ^h Systemic inflammation assessment includes testing for procalcitonin, WBC, and CRP (see Table 7-1).
- ⁱ Illness severity scores include CLIF-C OF score, CLIF-C AD score, CLIF-C ACLF score, MELD score, and Child Pugh score (see Appendix 3 for illness severity scores).
- ^j Biomarker retains will be drawn for potential analysis of cytokines (interleukin [IL] 6 (IL-6), IL-8, IL-10, and tumor necrosis factor alpha [TNFα]) found in the blood which are significantly correlated with disease activity (see Table 7-1). All clinical blood samples will need to be drawn first before biomarker retains are drawn.
- ^k Findings from abdominal ultrasounds performed in the last 6 months will be recorded.
- ¹ Findings from endoscopic procedures performed in the last 6 months will be recorded.
- ^m Full physical examination (excluding breast and genitourinary examination).
- ⁿ Physical examination performed on Month 6 only.
- EQ-5D-5L health questionnaire and optional collection for blood biomarker retains on Months 1, 3, 6, and 9. All clinical blood samples will need to be drawn first.
- ^p Assessed on Day 11 and Months 1, 3, 6, and 9.
- ^q Assessed on Months 3 and 6.
- ^r Month 12 Visit only.

24-Sep-2020 87 ę 74 Effective Date Page IG1601 - Prevention of Mortality with Long-Term Administration of Human Albumin in Subjects Effective Status Version 6.0 with Decompensated Cirrhosis and Ascites Number GLB-PRT-ALB-IG1601 Bioscience Industrial Group **GRIFOLS**

Appendix 2 European Association for the Study of the Liver Clinical Practice Guidelines on the Management of Ascites/International Club of Ascites

Uncomplicated ascites: Ascites that is not infected and which is not associated with the development of the hepatorenal syndrome. Ascites can be graded as follows:

Grading of Ascites	and Suggested	Treatment
---------------------------	---------------	-----------

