9.1 Primary Endpoint

9.1.1 Time to Liver Transplantation or Death Through 1 Year After Randomization

Time to one-year transplant-free survival will be calculated as the earlier of [(date of liver transplantation or date of death) – randomization date + 1] for those subjects who died or had a liver transplant within the analysis period. Subjects who neither died nor had a liver transplant within the analysis period will have their time to event censored at the earlier of the following times:

- Date of last contact.
- Cut-off date for analysis.

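### The last-contact list in SAP 6.1.4 is looser than its own proof-of-life condition and, programmed literally, can credit unconfirmed event-free time in the primary endpoint

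*SAP*

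**What the plan says.** SAP 6.1.4 defines last contact as the last observation in the eCRF or other study data "which provide proof of being alive. The following lists the dates to be considered for status of being alive". Two entries on the list that follows matter here:

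- "Date of subject completion or withdrawal", with no condition on the reason or on whether anyone was in contact with the subject that day.
- "Date of liver transplant/vital status assessment, with survival status not" *Dead*. Status *Alive* is not required, and an unknown or blank status is not excluded.

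This date sets the censoring time. SAP 6.1.1 says that subjects without an event "will have their time to event censored at the earlier of date of last contact or cut-off date for analysis". SAP 9.1.1 applies the same rule to the primary endpoint ("Subjects who neither died nor had a liver transplant within the analysis period will have their time to event censored at the earlier" of last contact and cut-off), and SAP 9.2.1 to 9.2.5 apply it to the five survival secondaries. The 1-year cut-off in SAP 9 is the randomization date plus 361 days.

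After early discontinuation, transplant and vital status are sought at Months 3, 6 and 12 (SAP 5.2.7). Protocol 5.3.5 puts this on a best-effort footing: "All efforts should be made to collect the vital status of the subject".

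**The concern.** The condition and the list can give different answers for the same subject. A status that was never established fails the proof-of-life condition but passes the *not Dead* entry. Likewise, a withdrawal date entered after contact was lost passes the list although nobody saw the subject that day. Suppose a subject leaves in Month 3, cannot be traced, and has a Month 12 status form dated near the cut-off without a confirmed status. The list read literally would censor that subject as event-free for almost the full year.

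Such subjects would sit in the risk set as if known to be event-free, which lowers the Kaplan-Meier event rate. If their share differed by arm, the hazard ratio would shift as well. Different loss is possible in an open-label trial with 37 expected infusions on Albutein (SAP 8.4) and 14 scheduled visits on SMT (Day 1, Day 11, Months 1 to 12). None of the sensitivity analyses in SAP 9.1.3 varies the censoring rule, and the disposition summary in SAP 7.1 does not report unknown vital status by arm.

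The list also concerns only being alive. The composite endpoint needs the subject to be alive and transplant-free on the censoring date. For subjects still in the study, transplant, survival and cause-of-death data are scheduled only at Months 3, 6 and 12 (Protocol Appendix 1, where the footnote for the monthly visits reads "Assessed on Months 3 and 6").

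**Working it through.** **Inputs from the plan (SAP 6.2 and 9).** 1-year event rates are 46% on SMT and 31% on Albutein, exponential times, 205 subjects per arm, 20% dropout, and an analysis period of 362 days.

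**The plan's own figure.** HR = ln(0.69)/ln(0.54) = 0.3711/0.6162 = 0.6022, as stated.

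**Assumptions not in the documents.** A share p of subjects is untraceable, with loss uniform over the 362 days and independent of outcome. Each untraceable subject without an earlier event is credited to the cut-off, which is the worst case.

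**Step 1: hazards and full-follow-up event probability.** With λ = −ln(S)/365 and T = 362:

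- SMT: λ = 0.001688, λT = 0.6111, F = 1 − exp(−0.6111) = 0.457.
- Albutein: λ = 0.001017, λT = 0.3680, F = 1 − exp(−0.3680) = 0.308.

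**Step 2: chance that the event is seen before a uniform loss time.** q = 1 − F/(λT):

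- SMT: 1 − 0.4573/0.6111 = 0.252.
- Albutein: 1 − 0.3079/0.3680 = 0.163.

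**Step 3: 1-year rate read under literal programming.** Everyone without an observed event is carried to the cut-off, so Kaplan-Meier returns E = (1 − p)F + p·q:

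- SMT, p = 10%: 0.9 × 0.4573 + 0.1 × 0.2518 = 0.437.
- SMT, p = 20%: 0.8 × 0.4573 + 0.2 × 0.2518 = 0.416.
- Albutein, p = 10%: 0.293. Albutein, p = 20%: 0.279.

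Censoring at true last contact recovers about 46% and 31% under these assumptions.

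**Step 4: credited time.** Mean extra follow-up per lost, event-free subject is d = T·[1/a − F/a²]/(F/a), with a = λT. This gives 199 days on SMT and 192 days on Albutein.

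**Step 5: hazard ratio as a ratio of event rates.** Correct person-time per subject is E/λ. Literal programming adds p(1 − q)d, so the rate is E/[E/λ + p(1 − q)d]:

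| Arm | p | E | E/λ (days) | added days | rate per 1000 days |
|---|---|---|---|---|---|
| SMT | 10% | 0.4367 | 258.7 | 14.9 | 1.596 |
| SMT | 20% | 0.4162 | 246.5 | 29.8 | 1.506 |
| Albutein | 10% | 0.2934 | 288.6 | 16.1 | 0.963 |
| Albutein | 20% | 0.2790 | 274.4 | 32.1 | 0.910 |

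- Equal loss: 0.963/1.596 = 0.603 (10%) and 0.910/1.506 = 0.604 (20%).
- SMT 20%, Albutein 10%: 0.963/1.506 = 0.64.
- SMT 10%, Albutein 20%: 0.910/1.596 = 0.57.
- The same formula with SMT 5% and Albutein 2.5% gives 0.61, and with the shares reversed 0.59.

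**Step 6: events.** At p = 10% the observed SMT events are 205 × 0.4367 = 89.5, whichever censoring rule is used. The rule changes person-time, not the event count.

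**Step 7: false-positive rate when the true HR is 1.** A simulation with 400,000 subjects per arm and a Cox model, crediting to the cut-off, gave the following against a nominal 2.5% in Albutein's favour:

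- Dropout 15% SMT and 25% Albutein: HR 0.985 if a quarter of dropouts have unknown status, and 0.95 if all do. The false-positive rate is 3.1% and 5.4%.
- Dropout 10% and 30%, all unknown: HR 0.89, false-positive rate 11.6%.
- Dropout 25% and 15%, all unknown: HR 1.06, false-positive rate 0.9%.

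Crediting only to the next Month 3, 6 or 12 assessment, instead of the cut-off, moves the HR by about 0.04 at most.

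**The case against.** The strongest reply is that the opening sentence of SAP 6.1.4 governs the list. An unknown status is not proof of life, so a programmer who reads the whole definition would not count it. That stands as the better reading, but the list is what gets coded, and it does not say so.

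A reader might infer that subjects of unknown status will in fact be counted as event-free. The documents do not support that. They do not show the response options on the vital-status page, nor how a withdrawal date is assigned when contact is lost. Lost to follow-up is not among the six withdrawal reasons in Protocol 5.3.3, and a subject who withdraws in person is alive that day. Protocol 5.3.5 also asks for a discontinuation visit, preferably within a week of withdrawal, for those who received the product. The withdrawal entry therefore matters only for administrative dates, usually with a much shorter gap than the 190 to 200 days above.

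A reader might also infer that the rule hides events. It does not: an event after contact is lost goes unobserved under either censoring rule.

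Nor do the documents support the idea that transplants are widely missed. The endpoint uses the transplant's own date (SAP 9.1.1), and planned visits continue after transplant (Protocol 5.3.2). The gap is mainly for subjects later lost.

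Finally, dropout is not the same as untraceable, because status is sought after discontinuation. The 20% case is an upper scenario, and the documents do not indicate which arm would lose more.

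**Conclusion.** The wording defect is real and should be fixed; a bias in the primary result is not shown. The list in SAP 6.1.4 is looser than its own condition, and it sets the censoring time for the primary and five survival secondary endpoints.

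At worst, with every untraceable subject carried to the cut-off, the SMT 1-year event rate reads about 44% (10% untraceable) or 42% (20%) instead of about 46%. The HR stays near 0.60 with equal loss. Reaching about 0.57 or 0.64 needs a two-fold difference in loss between arms at the 10% to 20% level, and the shift can go against Albutein as well as for it.

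All of this rests on the plan's event rates, uniform loss independent of outcome, and literal programming. The share of subjects affected is unknown from the documents and could be close to zero.

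**What to change.** Change the SAP wording before database lock:

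1. In SAP 6.1.4, let a vital-status assessment count only when survival status is *Alive*, in place of *not Dead*.
2. In the same list, count a completion or withdrawal date only when contact with the subject on that date is documented.
3. For the transplant-or-death endpoints (SAP 9.1.1, 9.2.2 and 9.2.4), censor subjects lost to follow-up at the last date on which they were known to be alive and transplant-free.

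No new eCRF item is needed. SAP 12 already speaks of most patients as enrolled, so adding a monthly transplant question now would be costly and might come too late. The price of the three changes is slightly shorter censoring times and a slightly higher reported event rate. Sample size, event target and stated power do not change.
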